## ***Sample Size***

---

### **Trial 1 (Normal hospital diet vs. Oral Supplements).**

We plan to randomise at least 6000 patients divided equally between the two groups which will provide us with at least 80% power to detect an increase in the proportion of patients surviving free of dependency (Modified Rankin <3) from 52% to 56% when the null hypothesis is rejected at p-values of 0.05 and below (i.e.  $\alpha = 0.05$ ,  $\beta = 0.2$ ).

### **Trial 2 (Immediate tube vs. Delay).**

We plan to randomise at least 2000 patients divided equally between the two groups which will provide us with at least 80% power to detect an increase in the proportion of patients surviving free of severe disability (Modified Rankin <4) from 30% to 36% when the null hypothesis is rejected at p-values of 0.05 and below (i.e.  $\alpha = 0.05$ ,  $\beta = 0.2$ ).

### **Trial 3 (NG vs. PEG).**

We plan to randomise at least 1000 patients divided equally between the two groups which will provide us with at least 80% power to detect an increase in the proportion of patients surviving free of severe disability (Modified Rankin <4) from 30% to 39% when the null hypothesis is rejected at p-values of 0.05 and below (i.e.  $\alpha = 0.05$ ,  $\beta = 0.2$ ).

We plan to continue to randomise patients into each of the three trials until we have achieved these minimum sample sizes in all three trials. Thus it is likely that we will exceed these sample size estimations in two of the trials to allow us to detect more modest treatment effects. Our Data Monitoring Committee may advise us to stop or prolong randomisation in any one of the three trials depending on the results of their confidential interim analyses.

## ***Pre-specified Sub-group Analyses***

---

We plan to explore other questions within The FOOD Trial, accepting that we may have insufficient power to come to definite conclusions at least without combining our data with those from other trials in a meta-analysis. We will address the following hypotheses:

- That the benefit of any feeding regime will depend on the patients' nutritional status at randomisation. Thus we plan to examine the effects of different feeding regimes in those classified as undernourished, normal and overweight at randomisation.
- That any benefit from a specific feeding regime will be influenced by the severity of the patients' stroke. We will therefore examine the effect of treatment in patients with mild, moderate and severe strokes as defined by their predicted prognosis at randomisation.
- That any benefits of oral supplements may be influenced by the nutritional support patients have received prior to randomisation. We will therefore examine separately the effect of oral supplements in patients randomised in Trial 1 initially or after having been first randomised in Trial 2 or 3.
- That the balance of risk and benefit of early initiation of tube feeding will depend on the type of tube feeding. We will therefore examine the difference in outcome between:
  1. Those randomised between immediate feeding via an NG tube vs. Delayed tube feeding for at least a week and hydration using parenteral fluids.
  2. Those randomised between immediate feeding via a PEG tube vs. Delayed tube feeding for at least a week and hydration using parenteral fluids.
- That feeding via an NG tube may be more appropriate than PEG for early tube feeding but that later feeding via a PEG tube will have advantages over that via an NG tube. Thus we will compare the outcomes of patients randomised between NG and PEG within the first week of admission and those randomised later.
- That a delay in starting feeding may lead to a worsening nutritional status which is impossible to compensate for later. Therefore we plan to examine the effectiveness of our various feeding regimes in patients randomised within a week of their stroke with those randomised after a week, allowing for pre-randomisation feeding and nutritional status.

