### **Immediate tube feeding vs. Delay tube feeding for at least a week and hydrate using parenteral fluids.**

If randomised to immediate tube feeding, the clinician may choose the type of tube or alternatively co-enrol the patient into Trial 3 (NG vs PEG). The tube feeding should be started as soon as possible and certainly within three days of randomisation. The liquid feed would be that normally used at that institution and given in consultation with a dietitian.

Patients randomised to delayed tube feeding should not have tube feeding started for at least a week and should be hydrated using parenteral fluids (IV or SC) given according to local protocols. The randomising clinician decides if and when tube feeding should start after the week has elapsed.

Inevitably, some patients may be taking some oral fluids or food whilst still being fed predominantly via a tube or whilst receiving parenteral hydration. Patients do not have to remain 'nil by mouth'.

**Trial 3** addresses the question *Is tube feeding via a PEG better than that via an NG tube?*

This is relevant to all stroke patients who cannot safely take adequate diet or fluids orally. We plan to randomise patients within the first month of the hospital admission between:

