## ***Co-enrolment - Randomising a patient into more than one of these three trials.***

---

We encourage clinicians to co-enrol their patients into more than one of the trials since this will:

- Maximise recruitment since patients are not ineligible because they have been previously been randomised into another of our three trials.
- Allow patients to contribute to more than one question.
- Allow us to formally investigate any interactions between the various feeding policies.

Thus patients may be co-enrolled:

- at the same time in Trial 2 (Immediate tube vs. Delay) & Trial 3 (NG vs. PEG) if the randomising clinician is unsure both about the timing and type of tube feeding. Obviously, in this case all treatment options must be available to the randomising clinician.
- sequentially in Trial 2 (Immediate tube vs. Delay) then Trial 3 (NG vs. PEG) if the patients swallowing does not recover.
- sequentially in Trial 2 (Immediate tube vs. Delay) then Trial 1 (Normal hospital diet vs. Oral Supplements) if the patients swallowing improves.
- sequentially in Trial 3 (NG vs. PEG) then Trial 1 (Normal hospital diet vs. Oral Supplements) if the patients swallowing improves.
- a patient could even enter Trial 2 (Immediate tube vs. Delay) in the first week, Trial 3 (NG vs. PEG) if they are persistently dysphagic and then Trial 1 (Normal hospital diet vs. Oral Supplements) when their swallowing improves, if the clinician was uncertain about all three questions.

Of course, patients cannot be randomised twice in the same trial during the course of their hospital admission. To enter a patient into another of the three trials later in the admission, the randomising clinician would simply complete another randomisation form (Appendix A) and telephone the randomisation service again.

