**PRIOR to randomisation, did this patient receive:**

Any enteral tube feeds? YES  NO

**SINCE randomisation, has this patient received:** (please tick (✓) one box on each line)

- |   |                              |                             |                                   |
|---|------------------------------|-----------------------------|-----------------------------------|
| Any Parenteral Fluids   | YES  | NO  | If YES complete PARTS 1, 5, 6 & 7 |
| Any feeding via an NG Tube  | YES  | NO  | If YES complete PARTS 2, 5, 6 & 7 |
| Any feeding via another type of tube (e.g. PEG)                               | YES  | NO  | If YES complete PARTS 3, 5, 6 & 7 |
| Any normal hospital diet PLUS supplementary feed                              | YES  | NO  | If YES complete PARTS 4, 5, 6 & 7 |
| Normal hospital diet only   | YES  | NO  | If YES complete PARTS 5, 6 & 7    |
| Other (e.g. total parenteral nutrition), please specify:  |                              |                             |                                   |

For office use

If allocated feeding policy(ies) was(were) **not** followed please give reason(s) below:

For office use

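### The Trial 1 subgroup on prior nutritional support is split by earlier trial entry, which pools Trial 2 Delay patients with patients allocated tube feeding and so dilutes the contrast it is meant to test

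*Protocol*

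**What the plan says.** Protocol, Pre-specified Sub-group Analyses, third hypothesis: "any benefits of oral supplements may be influenced by the nutritional support patients have received prior to randomisation". The split given for it compares "patients randomised in Trial 1 initially or after having been first randomised in Trial 2 or 3".

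Protocol, Trial Design, sets out what the earlier trials allocate:

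- Trial 2, Delay arm: "Patients randomised to delayed tube feeding should not have tube feeding started for at least a week and should be hydrated using parenteral fluids". Some oral intake is permitted meanwhile, and after the week the clinician decides whether and when to tube feed.
- Trial 2, Immediate arm: "The tube feeding should be started as soon as possible and certainly within three days of randomisation".
- Trial 3: both arms (PEG and NG) are tube feeding, with the same instruction on starting.

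Protocol, Co-enrolment, lets patients be randomised "sequentially in Trial 2 (Immediate tube vs. Delay) then Trial 1 (Normal hospital diet vs. Oral Supplements) if the patients swallowing improves". This route is open to both Trial 2 arms. A similar route leads from Trial 3 to Trial 1.

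The Hospital Discharge Form (Appendix C) asks whether, before randomisation, the patient received "Any enteral tube feeds". Parts 2 and 3 of the form record tube insertion and removal dates after randomisation.

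**The concern.** The hypothesis names one variable, support received, and the split uses another, entry to an earlier trial. The two would agree only if entering Trial 2 or 3 meant being fed. Trial 2 randomises that very question, so its two arms have contrasting feeding histories by design, yet both go into one stratum.

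The initial-entry stratum is not uniform either. Trial 1 accepts patients up to 30 days after admission, including those who have regained a safe swallow, so it can hold patients who were tube fed outside the trials.

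What the split does separate fairly well is earlier dysphagia. Nearly all later entrants had it, whereas most initial entrants could swallow on admission. A difference in supplement effect between the strata could be read as an effect of prior feeding when it reflects dysphagia or stroke severity, and a real dependence on prior feeding would be understated.

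**Working it through.** The protocol gives no figure for this subgroup, so there is none to reproduce. The following is an illustration under stated assumptions.

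**Inputs from the protocol (Sample Size).** Trial 2: at least 2000 patients, divided equally, so 2000/2 = 1000 in Delay. Trial 3: at least 1000 patients.

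**Assumptions, not in the protocol.** Every Trial 2 or Trial 3 participant is equally likely to go on to Trial 1. Any overlap between Trials 2 and 3 is entry at the same call. Prior support is reduced to tube fed, yes or no, before Trial 1.

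**Step 1: Delay share of the later-entry stratum.** Share = 1000 / (2000 + 1000 − overlap).

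- No overlap: 1000/3000 = 33%
- Overlap of 500: 1000/2500 = 40%
- All Trial 3 patients also in Trial 2: 1000/2000 = 50%

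**Step 2: how much of a true difference the split shows.** Let the supplement effect be d1 in patients tube fed before Trial 1 and d0 in the rest, with D = d1 − d0. Let f be the share of the later-entry stratum not tube fed, and g the share of the initial-entry stratum that was.

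- Later-entry effect: (1 − f)·d1 + f·d0
- Initial-entry effect: g·d1 + (1 − g)·d0
- Difference: (1 − f − g)·D

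With the stratum proportions held fixed, the number of patients needed for the same power rises by 1/(1 − f − g)².

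**Step 3: results.**

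| Assumption | Delay share 33% | 40% | 50% |
|---|---|---|---|
| No Delay patient tube fed, g = 0 | 67% visible, 2.25 times the patients | 60%, 2.78 times | 50%, 4 times |
| Half of Delay patients tube fed, g = 0 | 83%, 1.44 times | 80%, 1.56 times | 75%, 1.78 times |
| No Delay patient tube fed, g = 10% | 57%, 3.11 times | 50%, 4 times | 40%, 6.25 times |

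In the second row f is half the Delay share (for example, 0.5 × 33% = 16.7%, and 1 − 0.167 = 83%). Delay patients who entered Trial 3 later would have been allocated tube feeding, which also lowers f.

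**Step 4: does another reading of the split avoid this?** If the text means three strata (initial, after Trial 2, after Trial 3), the problem moves to the Trial 2 stratum, where Delay and Immediate are still pooled.

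**The case against.** A reader might infer that the Delay patients were left unfed and that the analysis can neither confirm nor refute its hypothesis. The documents support neither. Delay means no tube feeding for a week or more; oral intake is allowed, and tube feeding may start later, before Trial 1. The arithmetic shows dilution, with half or more of the contrast surviving when nobody in the initial-entry stratum was tube fed, and not its loss.

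Three further points count in the protocol's favour.

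- The Introduction and Co-enrolment sections plan a formal look at how the feeding policies interact. Among patients who go from Trial 2 to Trial 1, that would compare Delay with Immediate using two randomised factors. The last subgroup hypothesis also adjusts for feeding before randomisation. This stands as partial cover, but neither analysis is tied to the hypothesis at issue, which fixes its own split.
- Earlier trial entry is known before Trial 1 allocation. The feeding data come from a form completed from the notes at discharge, after an allocation that staff know. This stands, and it argues against replacing the split with tube fed, yes or no. That replacement would also put Delay patients never tube fed together with patients who ate normally from admission, and it would stay confounded with dysphagia.
- The protocol calls these subgroup analyses exploratory and accepts that they may lack power. This limits the consequence, but it does not justify a split that misses its own variable.

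The wording of the prior-feeding item on the form is a small matter. Neighbouring items refer to the first randomisation, so the likely meaning is clear, though not stated.

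**Conclusion.** The mismatch between hypothesis and split is real and lies in what the protocol fixes, not in detail left to an analysis plan. As written, the later-entry stratum combines patients allocated to wait for tube feeding with patients allocated to receive it, so the comparison dilutes the contrast of interest and largely marks earlier dysphagia.

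The size is not known from the protocol. The range of 67% to 50% of a true difference visible rests on three assumptions: equal onward entry to Trial 1, no tube feeding of Delay patients before Trial 1, and none in the initial-entry stratum. It improves to 83% to 75% if half the Delay patients were tube fed, and worsens to 57% to 40% if 10% of initial entrants were tube fed outside the trials.

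Severity is minor. No primary outcome, sample size or main comparison is affected.

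**What to change.** Define the strata by earlier randomised allocation, which is known before Trial 1 allocation:

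- (a) Trial 1 only;
- (b) earlier Trial 2 Delay, without a later, separate entry to Trial 3 (Delay patients entered in Trial 3 at the same call stay here);
- (c) earlier Trial 2 Immediate, or Trial 3 otherwise.

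Report the supplement effect in each stratum with a treatment-by-stratum interaction. Take (b) versus (c) as the main contrast for prior feeding, because both groups were dysphagic, and state that comparisons with (a) are confounded with dysphagia. The (b) versus (c) contrast is better protected but not fully randomised: (c) includes Trial 3 patients and those Delay patients whose swallowing problem lasted long enough for a later Trial 3 entry.

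Use tube feeding actually received before Trial 1 as a sensitivity analysis, from the prior-feeding item and the Part 2 and Part 3 dates set against the Trial 1 randomisation date. Reword the prior-feeding item to name the first randomisation.

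The cost is a reworded subgroup, one clarified form item, and smaller strata in an exploratory analysis. No additional patients or data items are needed.

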## TRIAL ORGANISATION

---

### *Data Monitoring Committee*

---

The Data Monitoring Committee comprises: Professor [name] (London), Professor [name] (Aberdeen, Chair), Professor [name] (Edinburgh) and Dr [name] (Edinburgh).

During the period of recruitment into the trial, interim analyses of the proportion of patients surviving free of dependency/severe disability as well as data available on other major outcome events will be supplied, in strictest confidence, to the chairman of the Data Monitoring Committee, along with any other analyses that the Committee may request. In the light of these analyses, the Data Monitoring Committee will advise the chairman of the Steering Committee if, in their view, the randomised comparisons have provided both (i) 'proof beyond reasonable doubt' that for all, or some, the intervention is clearly indicated or clearly contra-indicated and (ii) evidence that might reasonably be expected to materially influence patient management in normal practice. Appropriate criteria of proof beyond reasonable doubt cannot be specified precisely, but some members of the committee have expressed sympathy with the view that a difference of at least 3 standard deviations in an interim analysis of a major outcome event

may be needed to justify halting, or modifying, such a study prematurely. If this criterion were to be adopted, it would have the practical advantage that the exact number of interim analyses would be of little importance, and so no fixed schedule is proposed. The Steering Committee can decide whether to modify intake to the trial (or seek extra data). Unless this happens, however, the Steering Committee, the collaborators and central administrative staff will remain ignorant of the interim results.

## ***Publication of the Trial Results***

---

All publications relating to the main trial will be published in the name of the International Stroke Trials (IST) Collaboration - FOOD.

Abstracts relating to the main study will be submitted as the International Stroke Trials (IST) Collaboration - FOOD along with the presenter's name.

Papers and abstracts relating to 'Add-on' studies will be in the name of those collaborators who took part or the group's name, but recognise the input of the entire Collaboration by putting 'part', 'member' or 'on behalf of' the International Stroke Trials (IST) Collaboration - FOOD.

Anyone wishing to use the data generated from this trial for higher degrees, PhDs etc. must first seek the permission of the Steering Committee. All papers must be approved by the Steering Committee prior to submission for publication. Anyone wishing to use the data in this way, will be asked to sign a confidentiality agreement which will prevent them from publishing the data until the results of the main trial have been published.

No group of collaborators should publish the results of any sub-study which splits patients by treatment allocation without the agreement of the Steering Committee, on behalf of the other members of the Collaboration. Studies which report any of the process or outcome data collected as part of the main study must acknowledge the collaboration as an author e.g. Smith on behalf of the International Stroke Trials (IST) Collaboration - FOOD.

## APPENDICES: A TO G

---

# APPENDIX A: Randomisation Form

## The International Stroke Trials Collaboration (Feed Or Ordinary Diet)

### RANDOMISATION FORM

**Do NOT randomise unless you are uncertain about the best feeding policy for your patient**

PLEASE BE READY TO PROVIDE THE FOLLOWING INFORMATION WHEN YOU MAKE THE RANDOMISATION TELEPHONE CALL ON

Has this patient been randomised into the FOOD trial before? No  (KEY 0) Yes  (KEY 1)

**HOSPITAL DETAILS:**

Country:   
 Hospital Name:   
 Name of responsible Consultant:   
 Randomising doctor:

Country number:   
 Hospital number:   
 Consultant number:

**Consent:** Has consent been given? Yes  (MUST be Yes) (KEY 1)

**PATIENT DETAILS:**

Family Name:  Given Name/s:   
 Date of Birth:  day  month  year Sex? Male  (KEY 1) Female  (KEY 2)  
 Date stroke symptoms first noticed:  day  month  year Date of admission:  day  month  year

**ABOUT THE PATIENT:** (the following questions will be asked by number)

- |   |                          |                          |                          |
|---|--------------------------|--------------------------|--------------------------|
|   | (KEY 1)                  | (KEY 0)                  | (KEY 9)                  |
|   | Yes                      | No                       | Don't Know               |
| 1 Did the patient live alone before admission?                            |  |  |  |
| 2 Was the patient independent in every day activities before this stroke? |  |  |  |

**ABOUT THE STROKE:** (the following questions will be asked by number)

- Is the patient:**
- |   |                          |                                  |
|---|--------------------------|----------------------------------|
|   | (KEY 1)                  | (KEY 0)                          |
|   | Yes                      | No                               |
| 3 able to talk and orientated in time, place and person? |  |          |
| 4 able to lift both their arms off the bed?              |  |          |
| 5 able to walk without help from another person?                |  |          |
| 6 able to swallow liquids safely?                               |  |          |
| 7 Do you think the patient is: (Tick one box only)       |                          |                                  |
| Under-nourished?                        | (KEY 1)                  | Normal?  |
|   |                          | (KEY 2)                          |
| Overweight?                             |                          | (KEY 3)                          |


8 Can the patient take adequate fluids orally?
 
 Yes  No
	
Yes 
 
(For Yes — Key 1) (For No — Key 0)
	
TRIAL 1 Randomise between tick                  Normal diet until discharge                   vs                  Normal diet PLUS oral supplements                   (prescribe 120ml 3x per day)

9 Within 1st week of admission are you uncertain whether to tube feed NOW or DELAY for at least a week?
 
 Yes  No
	
Yes 
	
TRIAL 2 Randomise between tick                  Immediate tube feeding                   vs                  Delay tube feeding for at least a week                   (and hydrate using parenteral fluids)

10 If you are going to start tube feeding NOW are you uncertain whether to use an NG or PEG tube?
 
 Yes  No
	
Yes 
	
TRIAL 3 Randomise between tick                  Nasogastric tube feeding                   vs                  PEG tube feeding 

11 If you are certain, which type of tube will you use?
	
NG  (Key 3)
 
PEG  (Key 4)
	

**Thank You** — Now please post or fax this form if you have used the automated randomisation service. Please keep the original for your records  
 [contact]

FOOD/SE/1/998

## NOTES

### ***Using the automated service***

Please note that you will not be able to make a reverse charge call to this service.

Remember to fax us the Randomisation Form every time the automated service is used. Our fax number is [contact].

If you would like to practice using this service, please call the number provided on the front of the FOOD manual.

If you experience any difficulties with this service please fax us the completed Randomisation Form and we will return it to you with the treatment allocation clearly marked.

